Other research reference	
number(s) (if applicable)	
Full (Scientific) title	Variations in the organisation of Early Pregnancy Assessment Units
	(EPAUs) in the UK and their effects on clinical, service and patient-
	centred outcomes
Health condition(s) or	Early Pregnancy
problem(s) studied	Multi mathada annraach
Study Type i.e. Cohort etc	Multi-methods approach 6,800
Target sample size	6,800
STUDY TIMELINES	
Study Duration/length	24 months
Expected Start Date	01/11/15
End of Study definition and	The end of the study will be defined as the last 26-week/3-month
anticipated date	follow-up visit for a participating patient. The study will be considered
	closed when the last patient has reached this time-point, all data are
	complete and all data queries have been resolved.
	Anticipated end date: 31/10/17
Koy Study milestones	First patient recruitment: 10/01/17
Key Study milestones	rist patient reciditment. 10/01/1/
FUNDING & Other	
Funding	Health Services and Delivery Research Programme
KEY STUDY CONTACTS	
Chief Investigator	[name]

Elizabeth Garrett Anderson Wing
University College London Hospital
[name]
[name]
[contact]
Email: [contact]

KEY ROLES AND RESPONSIBILITIES

SPONSOR: The sponsor is responsible for ensuring before a study begins that arrangements are in place for the research team to access resources and support to deliver the research as proposed and allocate responsibilities for the management, monitoring and reporting of the research. The Sponsor also has to be satisfied there is agreement on appropriate arrangements to record, report and review significant developments as the research proceeds, and approve any modifications to the design.

FUNDER: The funder is the entity that will provide the funds (financial support) for the conduction of the study. Funders are expected to provide assistance to any enquiry, audit or investigation related to the funded work.

CHIEF INVESTIGATOR (CI): The person who takes overall responsibility for the design, conduct and reporting of a study. If the study involves researchers at more than once site, the CI takes on the primary responsibility whether or not he/she is an investigator at any particular site.

1 INTRODUCTION

A recent NICE guideline on "Ectopic pregnancy and miscarriage" (CG154)¹ published in December 2012 emphasises the need for good quality research to establish the effectiveness of Early Pregnancy Assessment Units (EPAUs). EPAUs are dedicated units within NHS hospitals that provide specialist care to women in the first three months of pregnancy. Women who experience pain or bleeding in the first weeks of pregnancy or women with a previous miscarriage or ectopic pregnancy are routinely seen in EPAUs. While most NHS hospitals in the UK have an EPAU, there are considerable variations between EPAUs in the levels of care they provide and their accessibility to women. In addition, staffing levels vary considerably between the units. The most cost-effective organisational model for an EPAU is unknown.

Early pregnancy problems are very common with 20% of recognised pregnancies ending in miscarriage and 2% of pregnancies being complicated by an ectopic pregnancy. Given the variation amongst units, women are likely to have different experiences of the services and the care provided.

We recently completed a pilot study of seven EPAUs across London to compare several clinical and service outcomes in units with different organisational structures, staffing levels and ease of access.

The study showed differences in several important clinical outcomes between different units. We used these findings to plan a larger study, which is described in this protocol.

We propose to collect information about all women who present to a sample of EPAUs, with suspected complications of early pregnancy, for initial or follow-up visits.

The main outcome of interest is the number of women who require emergency admission and stay in hospital. This could be either because a diagnosis cannot be made with certainty in the EPAU clinic, or because of the need for further treatment.

In addition to the primary outcome we will:

- a) Examine the number of follow-up visits and ultrasound scans that are required to reach a diagnosis.
- b) Look at the number of surgical keyhole procedures that were performed for suspected ectopic pregnancy and the number of procedures which did not confirm this diagnosis.
- c) Record all women who had a burst ectopic pregnancy and required a blood transfusion.
- d) Collect and analyse information about women's experiences of the care they received in an EPAU and their satisfaction with it.
- e) Conduct workforce modelling of the most effective EPAU staffing configuration(s), based on the primary outcome.
- f) Conduct a cost-effectiveness analysis of alternative workforce models.

We have estimated that we need to include 44 EPAUs nationwide. We based our calculations on our findings from the smaller study, which showed that quality of care appears to be better in the units where senior doctors (consultants) tend to spend more time working with other staff members who are looking after pregnant women. We will ensure that the units included in the study represent a good mixture of units located within both different types of hospitals and different geographic areas within the UK. The study will last for 2 years.

The research team includes clinicians, academics, and lay members, and the conduct of the study will be overseen by a Study Steering Committee. The information obtained from this study will help to better organise EPAUs nationwide in order to ensure optimal clinical outcomes in the most cost effective way.

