9.3.2 Secondary outcome analysis

The analyses of the secondary outcomes (number of follow-up visits, non-diagnostic ultrasound scans, negative laparoscopies, estimated blood loss at surgery and ruptured ectopic pregnancies requiring a blood transfusion, patient satisfaction) will follow a similar pattern although the type of regression model will be tailored for the specific outcome measure (e.g. hierarchical Poisson/linear regression will be used to analyse number of follow-up visits). Regression modelling will also be used to analyse the effect of opening hours and service accessibility on the overall admission rates and other clinical outcomes. Again, the type of regression model will depend on the clinical outcome and opening hours / service accessibility will be treated as exposure variables.

Health Economic analysis

The economic evaluation will comprise two parts:

- a within-study analysis, and
- a longer-term, model based, analysis.

The within-study analysis will focus on the costs and outcomes during the study period and will be based on the data collected during the study. The longer-term model based analysis will supplement the study data with data from the literature, particularly on patient outcomes. These additional data will be used to estimate the cost-effectiveness of different staffing configurations when longer term outcomes are taken into consideration.

In each analysis we will examine the cost-utility of different skill-mix configurations for staffing EPAUs. Outcomes for each analysis will be 1) patient quality of life, measured as quality adjusted life years (QALYs) and 2) admissions avoided.

Costs will be estimated from a societal perspective (capturing costs to the NHS, social services and patients). Results will be reported as the incremental net benefit of the modelled skill-mix configurations, and incremental cost-effectiveness ratios.

Uncertainty will be captured in the analyses through probabilistic sensitivity analysis and reported using cost-effectiveness acceptability curves, showing the likelihood a particular skill-mix model will be cost-effective over a range of values of the societal willingness to pay for a QALY.

In this section, we detail how we will collect and analyse data for the economic evaluation and how this will link with the skill-mix modelling.

Skill-mix model development:

The services delivered by a given EPAU are determined by two broad factors:

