- 1. the workforce delivering the required care, and
- 2. the clinical approach used to deliver that care (for example the thresholds for certain tests to be offered may be different even in configurations where the staff make-up is similar).

Using the clinical and operational data collected as part of the cohort study of clinical outcomes, we will identify skill-mix models appropriate for further consideration in a costutility analysis. This first stage of analysis will define appropriate EPAU skill-mix configurations for assessment in cost-utility analysis. The set of alternative staffing configurations will be used to estimate the expected costs of different skill-mix models, based on what is already known about the studied EPAUs. These models will consider both skill-mix and other factors that determine the cost of delivery local services.

The costs for each EPAU to deliver services will also vary according to each configuration as these will be dependent on the make-up of the local workforce as well as the local costs of

premises and equipment. While care pathways may be consistent across the country as a result of the nationally adopted guidelines, the scale and size of each EPAU will be different due to the service requirement of each locality due to population size, epidemiological factors and local socio-economic characteristics (such as ethnicity, levels of deprivation and education). This means that the workforce size and EPAU cost required to meet the service requirement will be locally dependent, and we will account for variation in costs in the analysis.

Within the skill-mix model we will consider the level of consultant presence, as well as the number and grade of other clinical and support staff available. The costs of implementing any configuration will include both the quantity of each skill set (consultant, junior doctor, nurse etc) required and the coverage time for which they are required. Another important factor to consider in skill-mix models will be case mix. A complex case mix may create a workload equivalent to that in a bigger unit with a less complex or complicated case mix.

Development of optimal skill mix model to run

Cost-utility analysis overview:

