Using the skill-mix model analysis we will then evaluate the cost utility of the set of identified potentially optimal skill-mix configurations. This analysis will combine the results of the skill-mix modelling configurations (with associated costs), patient outcome data, patient resource use data and data on additional costs to patients, social services and the NHS not already captured in the EPAU unit configuration costs. Results of the economic evaluation will be reported in standard metrics, including:

- The incremental cost-effectiveness ratio (ICER) of an additional admission avoided, (cost per additional avoided)
- The ICER based on quality adjusted life years (cost per QALY gained), and
- the net benefit statistic.

Sensitivity analysis will be used to test assumptions about the model structure, to explore the generalizability of the results and to capture the underlying uncertainty in the sample data. Probabilistic sensitivity analysis will be used to capture the uncertainty arising from the sampled data, with model parameters defined as probability distributions and Monte Carlo simulations used to simulate repeated trials. Structural uncertainty in the model (for example, relating to variability in individual skill-mix configurations or local staff availability) will be explored using one-way and scenario analyses. Additional one and two-way analyses will be used to explore further the generalisability of the results.

Primary within-study analysis

The primary economic evaluation will be a within-study analysis. As described above, in the analysis we will estimate incremental cost-effectiveness ratios for the two main outcomes of interest, patient quality of life (in QALYs) and admission rates. These will be reported together with associated Bayesian credible intervals, based on the data collected in during

the study period. For this analysis data will be drawn as far as possible from the study data. Monte Carlo simulation methods will be used to construct a cost-effectiveness acceptability curve, based on the expected net benefit statistic, to estimate the probability that the intervention is cost-effective for a range of values of societal willingness to pay per QALY. We will also subject the results to extensive deterministic (one, two, and multi-way) sensitivity analysis.

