The analysis process will be as follows: Initial data exploration will be conducted using standard frequentist statistical approaches. First we will compare baseline costs and other factors between groups to determine if any of the baseline characteristics predict costs. Where there are differences appropriate methods will be used to standardise/adjust for these. Unadjusted costs and outcomes will be estimated and reported. Regression analyses will be used to adjust for differences in baseline characteristics and adjusted values will also be reported. Estimates of skewness will be calculated for all resource use variables. As resource use data are commonly skewed, appropriate regression methods will be required (eg GLM) to account for this.

We will explore whether there are baseline characteristics across each group that explain differences in costs. This will be used to explain how costs are linked to baseline characteristics and the intervention. This will help us understand skill-mix variation effects holding everything else constant. It can also help us understand what the drivers of patient costs are and whether they are associated with any between group differences. Coefficients and p-values will be reported for each model tested.

Once we have explored the data and assessed for any important difference in baseline characteristics cost-effectiveness analysis can be undertaken. Unadjusted data will be used for the cost-effectiveness analysis. Simulation methods as described by O'Hagan and others²² will be applied. As is common with healthcare data, costs are expected to be skewed due to a small number of patients who typically consume a disproportionately large level of resources. As a result, the assumptions required for standard statistical approaches based on normally distributed data do not hold. A Bayesian parametric approach to analysis of costs will be followed to address concerns arising from the expected non-normality of the data.

Changes in reported anxiety measured using the visual analog scale will also be evaluated. Anxiety measures will be taken at the baseline data collection point, at the end of the initial visit to the EPAU prior to discharge and then at any clinic follow-up appointments. In the absence of an accepted minimally important difference in anxiety scores a standardised scoring based on Cohen effect sizes will be applied, with 0.2 assumed to be 'small' effect size, 0.5 medium effect size and 0.8 a large effect.

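### Skill-mix configurations are screened partly on admissions and then scored on admissions avoided in the same 44 units, so the preferred one looks better than it is on average, and no planned step corrects this

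*Protocol*

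**What the plan says.** The skill-mix and economic strand runs in two steps.

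- **Aim.** Introduction, item e): "Conduct workforce modelling of the most effective EPAU staffing configuration(s), based on the primary outcome". The primary outcome is emergency admission.
- **Step 1, choosing.** Section 9.3.2, skill-mix model development: "Using the clinical and operational data collected as part of the cohort study of clinical outcomes, we will identify skill-mix models". This stage defines what enters the cost-utility analysis.
- **Step 2, scoring.** Section 9.3.2, cost-utility overview: the team will "evaluate the cost utility of the set of identified potentially optimal skill-mix configurations". The outcomes are patient quality of life "measured as quality adjusted life years (QALYs) and 2) admissions avoided".
- **Data for step 2.** For the within-study analysis, "For this analysis data will be drawn as far as possible from the study data", and "Unadjusted data will be used for the cost-effectiveness analysis".
- **Uncertainty.** "Probabilistic sensitivity analysis will be used to capture the uncertainty arising from the sampled data". Credible intervals and scenario analyses are also planned.

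Section 9.3.2 describes no hold-out units, cross-validation, resampling of the first step or shrinkage. The hierarchical model of section 9.3.1 is specified for the primary analysis, not for the cost-effectiveness estimates.

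**The concern.** If admissions help to decide which configurations count as promising, the ones retained are partly those whose units happened to have few admissions during data collection. Scoring them on the same admissions counts that luck as effect. Cost per admission avoided has admissions avoided as its denominator, so an inflated denominator makes the preferred configuration look cheaper per admission avoided than it is.

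A probabilistic sensitivity analysis that draws parameters for configurations already chosen is centred on the optimistic estimates. It widens the interval around them but does not move it.

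Section 3.2 makes finding the best skill mix, and recommending how UK units should be configured, stated objectives. These figures would feed that recommendation.

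**Working it through.** **Planning figures (section 9.1).** Inputs are 8.5% against 3.5%, 90% power, 5% significance (two-sided assumed), 22 units per side and ICC 0.04. With pooled variance and mean rate 0.06:

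n per side = [1.960·√(2·0.06·0.94) + 1.2816·√(0.085·0.915 + 0.035·0.965)]² / 0.05² = (0.658 + 0.428)² / 0.0025 ≈ 472.0, rounded up to 473.

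The total is 946, as stated. The design effect is 1 + 149·0.04 = 6.96. Then 473·6.96 = 3292 per side, and 3292/150 = 21.9, so 22 units. The planning figures reproduce, and the same clustering assumptions are used below.

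**Assumptions not in the protocol.** K configurations with the 44 units split as evenly as possible; 150 women in each unit; a 6% mean rate (midpoint of 8.5% and 3.5%); and the configuration with the lowest observed rate is the one preferred. ICC 0.01 is shown as a milder case.

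**Rough formula, no true difference.**
- Variance of a unit's observed rate = p(1−p)·[ICC + (1−ICC)/150] = 0.0564·(0.04 + 0.0064) = 0.00262, so the SD is 5.12 points.
- SE of a configuration mean = SD/√(44/K). For K=4 this is 5.12/√11 = 1.54 points; for K=8 it is 5.12/√5.5 = 2.18 points.
- The expected minimum of 4 standard normals is −1.03, and of 8 it is −1.42. The expected optimism is about 1.59 and 3.10 points.

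**Simulation.** Unit rates are in fact right-skewed, so beta-binomial simulation is preferred. It gives slightly smaller values. Optimism is the true rate minus the observed rate of the selected configuration, in percentage points:

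| True rates | K | ICC 0.04 | ICC 0.01 |
|---|---|---|---|
| all 6% | 2 | 0.6 | 0.4 |
| all 6% | 4 | 1.5 | 0.9 |
| all 6% | 8 | 2.8 | 1.8 |
| 7.0, 6.5, 5.5, 5.0% | 4 | 1.3 | 0.6 |
| 8.5, 6.8, 5.2, 3.5% | 4 | 0.6 | 0.1 |
| 8.5, 3.5% | 2 | about 0 | about 0 |

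With no true difference, apparent admissions avoided against the remaining configurations are roughly the optimism times K/(K−1). At ICC 0.04 this gives 1.52·4/3 = 2.0 points for K=4 and 2.77·8/7 = 3.2 points for K=8. The design difference is 5 points.

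**Does a correction work?** Units were resampled within configurations and the lowest-rate configuration was re-selected in each replicate. Replicate optimism is the full-data rate of the configuration selected in that replicate minus its rate in the replicate. The average was added to the observed lowest rate. At ICC 0.04 the remaining optimism fell from 1.5 to about 0.6 points (K=4, no true difference), from 2.8 to about 1.3 (K=8, no true difference), from about 1.2 to 0.4 (K=4, 7.0 to 5.0%) and from 0.6 to about 0.1 (K=4, 8.5 to 3.5%). The correction is partial but removes more than half.

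**The case against.** **No pick-the-lowest rule is written.** A reader might infer that one winner is chosen on observed admissions. The methods do not say that. Step 1 reads "we will identify skill-mix models appropriate for further consideration in a costutility analysis", several configurations go forward, and staff grades, coverage time and case mix are also considered. This stands, and it makes the figures above illustrations. It does not remove the problem: keeping only configurations judged possibly optimal, and then recommending among them, is still selection, and item e) names the primary outcome as its basis.

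**The calculation does not isolate the screening step.** Taking the best of K fixed configurations gives the same optimism even if the list was locked beforehand. This is correct. Locking the list alone is therefore not a sufficient remedy.

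**The large figures need configurations that are truly alike.** Also correct. The protocol plans for a real difference, and the pilot admission rates ran from 2.3% to 9.7%. With wide true differences the optimism is small.

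**Not every economic result is inflated.** A reader might infer that the acceptability curve must favour the chosen configuration too. It is defined on willingness to pay per QALY. EQ-5D comes only from consenting women and detailed resource use from about 320 questionnaires, so the overlap of data is complete only for admissions. A configuration with few admissions may also cost more to staff.

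**Detail may come later.** Section 12 promises a detailed analysis plan before analysis, and it could contain a correction. But the protocol itself fixes the two steps, their shared data source and the use of unadjusted data, so the plan would have to change or supplement what is stated.

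**Conclusion.** The point holds for the secondary skill-mix and economic strand. As written, admissions in the same 44 units contribute to identifying the configurations and then to scoring them, and no step corrects for this. The admission rate of the preferred configuration is therefore optimistic in expectation, as are its admissions avoided and cost per admission avoided.

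Under the stated assumptions at ICC 0.04, the size ranges from near zero (two configurations at the design rates) to 2.8 points (eight identical configurations). For four configurations it is 0.6 to 1.5 points. The number of configurations and the rule for preferring one are assumptions, so none of these figures is a prediction for this study.

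The documents do not support the stronger reading that the chosen configuration is certain to be overrated, or that all economic outputs are biased in its favour. QALYs and the acceptability curve are affected only as far as they depend on admissions. The primary hypothesis test and the sample size are unaffected.

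**What to change.** Change section 9.3.2 in two ways.

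1. Define the candidate configurations from staffing and operational data (consultant time, number and grade of other staff, opening hours) and record the list before admissions are examined. This removes outcome-driven grouping. It does not remove the optimism of reading off the best of several.
2. For whichever configuration is named best, report admissions avoided and cost per admission avoided corrected for selection. Resample whole units and repeat the selection step in every replicate. Alternatively, use shrunken configuration estimates from a hierarchical model. Carry the resulting uncertainty into the probabilistic sensitivity analysis.

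The cost is protocol wording and some extra computing, with no new data. The downsides are that the correction is only partial when configurations are truly alike, and that the preferred configuration will look less favourable and less certain.
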